3.1 PRIMARY ENDPOINT

(Efficacy) Frequency of Implant Passing Events

Frequency of implant passing events will be reported for all subjects. Failure in this endpoint is defined, on a per patient basis, as the presence of one or more spontaneous implant passing events. A single event may be one or more clips or sutures being spontaneously passed by the patient (*i.e.*, not removed by medical staff).

Frequency of implant passing (either clips or sutures) will be explicitly collected at each follow-up visit; however, events may be reported between visits or during unexpected visits. When implant passing is reported, subjects will be asked to collect and provide passed implants, and an in-person evaluation will be performed. This will involve a visual cuff closure and healing assessment.

In the final analysis of this primary efficacy analysis, the rate of implant passage will be reported through six weeks. The primary objective of this endpoint is to observe a study population failure rate of less than 5% and is neither statistically-driven nor comparative.

(Safety) Frequency of Vaginal Cuff Dehiscence

Vaginal cuff dehiscence is defined as rupture of the surgical wound requiring surgical re-intervention. The proportion of subjects who experience vaginal cuff dehiscence up to six weeks after surgery will be evaluated. In the final analysis of this primary safety endpoint, failure will be reported, and test and control groups will be compared using Fisher's exact test to assess for a possible difference between groups.

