7 PARTICIPANT DISCONTINUATION, WITHDRAWAL, AND LOSS TO FOLLOWUP

7.1 DISCONTINUATION OF STUDY INTERVENTION

As this study involves a single surgical treatment, discontinuation from study test intervention occurs in the circumstance of an additional procedure required to address failed cuff closure, or dehiscence. In this case, cuff closure with the test or reference article will have failed and will be reflected in cuff closure failure rate reported the secondary study endpoint analysis. If a subject receives an additional procedure to address vaginal cuff dehiscence, they will re-start study follow-up, including one week, six week, and six month in-person visits and a 12-month phone call. All secondary endpoint data collection will be re-performed according to the new follow-up schedule and will be included in secondary endpoint analysis.

In any circumstance in which an investigator determines it necessary to discontinue subject participation for reasons other than vaginal cuff dehiscence, that subject will be discontinued from the study and may not be included in study analysis. The reason(s) for discontinuation will be documented on the End of Study CRF.

Overall study discontinuation and closure is further discussed in section 10.1.2.

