7.2 PARTICIPANT DISCONTINUATION/WITHDRAWAL FROM THE STUDY

Participants are free to withdraw from participation in the study at any time upon request. An investigator may discontinue or withdraw a participant from the study for the following reasons:

- Reported sexual activity prior to six-week follow-up;
- If any clinical adverse event (AE), abnormality, or other medical condition or situation occurs such that continued participation in the study would not be in the best interest of the participant; or
- If the participant meets an exclusion criterion (either newly developed or not previously recognized) that precludes further study participation.

Follow-up will continue for any subjects who are withdrawn from the study by an investigator for any of the above reasons. These subjects will remain part of the ITT population for the evaluation of the primary endpoint and will be included in the study safety population.

The reason for participant discontinuation or withdrawal from the study will be recorded on the End of Study Case Report Form (CRF). Subjects who sign the informed consent form and are randomized but do not receive the study intervention may be replaced. Subjects who sign the informed consent form, and

Protocol QD-PRO-045 Rev 005

are randomized and receive the study intervention, and subsequently withdraw, or are withdrawn or discontinued from the study, will not be replaced.

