9.3 POPULATIONS FOR ANALYSES

Intent-to-treat population (ITT): This population will include all subjects enrolled and randomized to test or reference treatment. Subjects will be analyzed according to the treatment to which they were randomized, regardless of the treatment they actually received.

Safety Population: This population will include all subjects enrolled and randomized to test or reference treatment. Subjects will be analyzed according to the treatment that they received; patients randomized to the reference arm that receive Zip-stitch™ will be included in the Zip-stitch™ safety population. Similarly, patients randomized to the Zip-stitch™ arm that receive sutures will be included in the reference safety population.

Primary and secondary efficacy analyses will be performed on the ITT population. All safety analyses will be performed on the Safety population.

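### Section 7.1 allows women discontinued by an investigator to be left out of the analysis, against 7.2 and 9.3, and one such exclusion can reverse the 5% implant-passing result

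*Combined protocol and SAP*

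**What the plan says.** Three places in the protocol bear on a woman whose participation an investigator ends.

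- **Section 7.1** first deals with dehiscence, where the woman restarts follow-up after re-operation. It then sets a general rule. The scope of the rule is wide: "In any circumstance in which an investigator determines it necessary to discontinue subject participation for reasons other than vaginal cuff dehiscence". Its consequence is stated as follows: "that subject will be discontinued from the study and may not be included in study analysis". It gives no list of reasons.
- **Section 7.2** lists the reasons for which an investigator may withdraw someone: sexual activity before the six-week visit, an exclusion criterion that is new or newly recognised, and a medical reason (the clause begins "If any clinical adverse event (AE), abnormality, or other medical condition or situation occurs such that continued participation in the study would not be", and goes on to her best interest). It then says: "Follow-up will continue for any subjects who are withdrawn from the study by an investigator for any of the above reasons". And: "These subjects will remain part of the ITT population for the evaluation of the primary endpoint and will be included in the study safety population".
- **Section 9.3** defines the ITT and the Safety populations with the same opening sentence, "This population will include all subjects enrolled and randomized to test or reference treatment", and has no exclusion for discontinuation. It adds: "Primary and secondary efficacy analyses will be performed on the ITT population. All safety analyses will be performed on the Safety population".

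Section 3.1 makes the primary efficacy result a bare observed rate: "The primary objective of this endpoint is to observe a study population failure rate of less than 5" per cent, with no statistical test. The primary safety endpoint there is the proportion with dehiscence up to six weeks.

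**The concern.** The same woman falls under two opposite rules. Each reason listed in 7.2 is also covered by the general rule in 7.1, unless the reason is dehiscence itself. One section keeps her in follow-up and in both populations. The other ends her participation and allows her to be left out. No section says which rule governs, who decides, or when the decision is made relative to unblinding.

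The treatment is a single operation, so discontinuation can only happen after exposure, often because of something that happened after surgery. Leaving such women out is selection after randomization on events that may not be independent of the outcomes being counted. It bears on the 5% comparison, on the dehiscence proportion, and on the adverse-event comparison between arms. Section 9.4.5 plans to tabulate adverse events that led to discontinuation, and the women in that row are among those whom 7.1 may leave out.

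**Working it through.** **1. The plan's own size.** Inputs from sections 4.1 and 9.2: 35 evaluable test women, 10% loss, 2:1 allocation. 35/0.9 = 38.9, so 39 test; 39/2 = 19.5, so 20 reference; total 59. This agrees with the stated target.

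**2. The two readings of the 7.1 clause.**

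| Reading of *may not* | Against 7.2 and 9.3 |
|---|---|
| must not be included | direct contradiction |
| might not be included | inclusion left to discretion, with no criteria and no named decision-maker, where 7.2 and 9.3 leave none |

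Neither reading agrees with the other two sections.

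**3. How few women decide the primary efficacy result.** The objective is met if passers/evaluable is below 5%. With 35 evaluable women, 1/35 = 2.86% meets it and 2/35 = 5.71% (exact 95% CI 0.7 to 19.2) misses it. Removing one passer takes one from numerator and denominator. At each size below, with the number of passers shown, that turns a miss into a success:

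| Test women analysed | All kept | One passer left out |
|---|---|---|
| 30 | 2/30 = 6.67%, missed | 1/29 = 3.45%, met |
| 35 | 2/35 = 5.71%, missed | 1/34 = 2.94%, met |
| 39 | 2/39 = 5.13%, missed | 1/38 = 2.63%, met |
| 40 | 2/40 = 5.00%, missed | 1/39 = 2.56%, met |
| 44 | 3/44 = 6.82%, missed | 2/43 = 4.65%, met |

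The reversal depends on the count. With three passers among 35, 3/35 = 8.57% becomes 2/34 = 5.88%, still missed. With one passer the objective is met either way.

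**4. Illustration over assumed true passing rates, n = 35.** With all women kept, the objective is met if X ≤ 1, where X is binomial(35, p). If one passer, where there is any, is left out, it is met if X ≤ 2.

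| Assumed true rate p | P(X ≤ 1), all kept | P(X ≤ 2), one passer left out |
|---|---|---|
| 5% | 47% | 75% |
| 8% | 22% | 46% |
| 10% | 12% | 31% |

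The true rates and the single exclusion are assumptions; the protocol gives neither.

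**5. What 9.4.10 would do.** Section 9.4.10 provides analyses of the ITT population with missing outcomes set to all successes and to all failures. Take two passers among 35, with one passer's outcome discarded and no other woman missing. If she stays in the ITT set as missing, the all-failure analysis gives (1 + 1)/35 = 5.7% and the all-success analysis gives 1/35 = 2.9%, so the doubt is visible. If 7.1 removes her from the set, every version gives 1/34 = 2.9%.

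Section 9.4.10 also leaves uncompleted six-week data out of the main denominator for women lost to follow-up. If the same is done for a woman whose participation is ended early, she leaves the headline rate even without formal exclusion.

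**The case against.** The strongest reply is that the statistical section already gives the answer. Section 9.3 (repeated in the synopsis) includes everyone randomized, 7.2 agrees, and 7.2 is the section headed for withdrawal from the study. On that view 7.1 holds one stray sentence, and an analyst working from section 9 would ignore it. This carries weight and shows which way the text should be made consistent. It does not remove the conflict, because the 7.1 sentence speaks of discontinuation from the study, which is the subject of 7.2, and no order of precedence is given.

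A second reply is that safeguards exist. Follow-up is done by a co-investigator blinded to treatment (4.1, 6.3), and an independent physician adjudicates safety events (10.1.5). Blinding limits differential exclusion between arms. It does less for the 5% comparison, which has no comparator: leaving out a passer lowers the rate whatever the assessor knows about treatment. Section 7.1 also does not require that the discontinuing investigator be blinded.

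Several stronger conclusions are tempting, and the documents do not support them.

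- *Dehiscence can remove a woman from the safety endpoint.* Section 7.1 exempts dehiscence. The remaining route is discontinuation for another event, with a later dehiscence then uncounted.
- *Such a woman is automatically dropped.* The clause can be read as permission only.
- *The row for adverse events leading to discontinuation would be empty.* That needs every such woman to be excluded. The tabulation uses the Safety population, so incomplete is the most that can be said.
- *Passing a clip leads to discontinuation, or marks poor healing.* Section 8.3.1 says passing alone is not an adverse event, and 2.3.2 reports no link between passing and compromised closure or healing.
- *A new post-operative infection must lead to withdrawal.* Section 7.2 requires that a newly met criterion also rule out further participation.

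**Conclusion.** The contradiction stands. The 7.1 clause, on either reading, permits exclusion after randomization that can depend on post-operative events, and it conflicts with the rule in 7.2 and the definitions in 9.3. This is a wrong rule rather than a missing detail.

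Its possible size is one woman deciding the primary efficacy result: 5.7% (missed) against 2.9% (met) at 35 evaluable test women. That figure assumes exactly two passers, one of whom is discontinued for some other reason and then left out. The documents do not show that this will happen or how often; the defect is that the plan allows it. For the dehiscence endpoint and the adverse-event tables, the consequence is possible undercounting of women discontinued for other reasons, and its size cannot be derived from the documents.

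**What to change.** 1. In 7.1, strike the second half of the sentence quoted above, the part about inclusion in analysis. State instead that all randomized women, including those discontinued by an investigator, are analysed in the ITT and Safety populations as in 7.2 and 9.3, and that all data collected on them are used.
2. State that a missing six-week outcome in such a woman is handled under 9.4.10, including the all-success and all-failure analyses. Section 9.4.10 names a single primary endpoint, so say whether these analyses also cover dehiscence.
3. Reconcile the 7.1 wording that ends participation with the 7.2 statement that follow-up continues, including for reasons that 7.1 covers and 7.2 does not list.

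The first two changes are a few sentences and should be made before unblinding. They add no visits for the reasons listed in 7.2, where follow-up is already required. For other reasons, the cost depends on how the third item is settled.

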7.2 PARTICIPANT DISCONTINUATION/WITHDRAWAL FROM THE STUDY

Participants are free to withdraw from participation in the study at any time upon request. An investigator may discontinue or withdraw a participant from the study for the following reasons:

- Reported sexual activity prior to six-week follow-up;
- If any clinical adverse event (AE), abnormality, or other medical condition or situation occurs such that continued participation in the study would not be in the best interest of the participant; or
- If the participant meets an exclusion criterion (either newly developed or not previously recognized) that precludes further study participation.

Follow-up will continue for any subjects who are withdrawn from the study by an investigator for any of the above reasons. These subjects will remain part of the ITT population for the evaluation of the primary endpoint and will be included in the study safety population.

The reason for participant discontinuation or withdrawal from the study will be recorded on the End of Study Case Report Form (CRF). Subjects who sign the informed consent form and are randomized but do not receive the study intervention may be replaced. Subjects who sign the informed consent form, and

Protocol QD-PRO-045 Rev 005

are randomized and receive the study intervention, and subsequently withdraw, or are withdrawn or discontinued from the study, will not be replaced.

7.3 LOST TO FOLLOW-UP

A participant will be considered lost to follow-up if she fails to return for any follow-up visit and is unable to be contacted by the study site staff. If a subject participates in all follow-up requirements through six months but does not participate in 12-month follow-up and is unable to be contacted by study site staff, their data will be reported through six months in the initial study reporting and may be imputed based on existing data as part of the 12-month supplementary report.

The following actions must be taken if a participant fails to return to the clinic for a required study visit:

- The site will attempt to contact the participant and reschedule the missed as soon as possible, will counsel the participant on the importance of maintaining the assigned visit schedule, and will ascertain if the participant wishes to and/or should continue in the study.
- Before a participant is deemed lost to follow-up, the investigator or designee will make every
 effort to regain contact with the participant (where possible, 3 telephone calls and, if necessary,
 a certified letter to the participant's last known mailing address or local equivalent methods).
 These contact attempts should be documented in the participant's medical record, study file,
 and ultimately on the end of study CRF.
- Should the participant continue to be unreachable, she will be considered to have withdrawn from the study with a primary reason of lost to follow-up.

8 STUDY ASSESSMENTS AND PROCEDURES

8.1 ENDPOINT ASSESSMENTS

The following will take place during the study, as outlined in the Schedule of Activities (SoA).

Prescreening

- Prescreening will take place prior to the approach of a potential subject.
- Each PI or a co-investigator surgeon will pre-screen potential subjects for conformance to
 inclusion and exclusion criteria after determining that a laparoscopic hysterectomy procedure is
 clinically appropriate and consistent with standard care.

Recruitment

- Recruitment will take place following prescreening and in parallel with hysterectomy scheduling.
- A potential subject's surgeon will inform potential subject of the existence of the trial once a potential subject has met all inclusion and exclusion criteria regarding study participation.

Screening

- Following initial study recruitment and displayed patient interest/willingness an investigator will screen subjects using patient medical history for conformance to all pre-operative study inclusion and exclusion criteria.
- An investigator will then complete the Pre-Enrollment screening form confirming subject conformance to all study inclusion and exclusion criteria.

Informed Consent

- Once a potential subject has been identified as satisfying the necessary pre-operative
 inclusion/exclusion criteria, an investigator will explain to the subject that they qualify for
 participation in this investigation. To avoid the potential for coercive influence by the study
 surgeon, the informed consent process will be performed by study personnel other than the
 investigator. Informed consent will be obtained using an IRB approved Informed Consent Form.
- Once a subject has provided Informed Consent, the site will schedule the procedure.

Baseline Data Collection

- Following completion of ICF, an investigator will complete baseline data collection according to the Baseline Data Collection form.
- Hemoglobin and pregnancy tests are to be performed prior to surgery as part of standard preoperative care for hysterectomy procedures. If not part of standard hospital care, pregnancy and hemoglobin tests are to be performed.

Intra-Operative Screening

- Results of hemoglobin and pregnancy test are to be re-confirmed as part of intra-operative screening.
- Enrollment (or exclusion) will occur during the laparoscopic hysterectomy procedure, following
 uterine excision, just before cuff closure. Reasons for mid-operative exclusion may include
 transition to laparotomy, surgeon's decision to close the cuff using suture with or without
 robotic assistance, realized subject satisfaction of exclusion criteria, or other complications.
- Investigator or coordinator will complete the Intra-Operative Screening Form during the procedure to confirm subject enrollment or exclusion.
- Once a subject has been enrolled, the subject will be assigned to a study group according to study randomization strategy.

Surgery - Cuff Closure

- Following intra-operative study enrollment, surgeon will close the cuff according to the subject's assigned study group.
- Surgeon will visually confirm the integrity of achieved vaginal cuff closure.
- The laparoscopic surgical video will be collected for reference.
- An investigator or coordinator will complete the Intra-Operative Report form and ensure surgeon evaluates cuff closure integrity and that laparoscopic video is saved.

One Week In-Person Follow-Up Visit

- This in-person follow-up visit should take place 7 ± 3 days of the study procedure and will include a vaginal examination for visual assessment of cuff closure.
- The subject will be assessed for study endpoints including implant passing, cuff closure evaluation, adverse events, pain, and dyspareunia.
- An investigator or coordinator other than that which provided cuff closure treatment will collect information for completion of case report forms by site coordinators as indicated in the SoA.

Six Week In-Person Follow-up Visit

This in-person follow-up visit should take place within six weeks ± five days of the study
procedure and will include a vaginal examination for visual assessment of cuff closure and
healing.

- Protocol QD-PRO-045 Rev 005
 - The subject will be assessed for study endpoints including implant passing, cuff closure and healing evaluation, adverse events, pain, and dyspareunia.
 - An investigator or coordinator other than that which provided cuff closure treatment will collect information for completion of case report forms by site coordinators as indicated in the SoA.

Six Month In-Person Follow-up Visit

- This in-person follow-up visit should take place within six months ± one week of the study procedure.
- The subject will be assessed for study endpoints including implant passing, cuff closure and healing evaluation, adverse events, pain, and dyspareunia.
- There will be a visual inspection of the vaginal cuff at this visit. An investigator or coordinator
 other than that which provided cuff closure treatment will collect information for completion of
 case report forms by site coordinators as indicated in the SoA.
- Data will be unblinded following completion of all six month follow-up visits.

12-Month Extension Period Call

- This assessment can take place in person or over the phone and should take place within 12 months ± four weeks of the study procedure.
- The subject will be assessed for study endpoints including implant passing, pain, dyspareunia, and adverse events.
- An investigator or coordinator other than that which provided cuff closure treatment will collect information for completion of case report forms by site coordinators as indicated in the SoA.

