4 STUDY DESIGN

4.1 OVERALL DESIGN

This randomized, controlled, blinded, prospective study will assess the safety and efficacy of the Zip-stitch™ Vaginal Cuff Closure System in achieving vaginal cuff closure following laparoscopic hysterectomy. This pivotal safety and efficacy study will begin at two sites and will be performed by a minimum of three surgeons but may be expanded to additional sites depending on enrollment. Additional sites may be inside or outside the United States.

The purpose of this trial is to evaluate the efficacy and safety of the Zip-stitch™ System. This will be accomplished by measure of the frequency of implant passing events and the frequency of postoperative vaginal cuff dehiscence, respectively. The observed rate of implant passing events will be numerically (not statistically) compared to a performance target of 5%.

A target of 59 women will be enrolled in a ratio of 2:1 test to reference (39 test and 20 reference subjects). This is based on a goal of 35 test subjects and an expected 10% of patients lost to follow-up. (See Section 9 for additional details).

During a pre-operative visit, a co-investigator surgeon may broach participation in this trial with candidate subjects. Potentially interested subjects will then be approached by a study coordinator or co-investigator surgeon other than their primary care provider to discuss study details and informed consent. Once obtained, surgery will be scheduled for interested participants.

Study enrollment will occur during surgery following satisfaction of all intra-operative exclusion criteria. This will take place after successful colpotomy, prior to initiation of vaginal cuff closure. Once enrolled, subjects will be randomized to receive cuff closure with either Zip-stitch™ or with VICRYL™ suture. Sealed randomization envelopes stratified by site and in variable block sizes will be provided in a blinded 2:1 ratio of test to reference cases. After randomization, the investigator surgeon will attempt to approximate and close the vaginal cuff using the assigned device. Integrity of the achieved closure will be visually assessed during each procedure, and laparoscopic video of cuff closure will be saved. Subjects will be blinded to the treatment they receive.

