5.2 EXCLUSION CRITERIA

An individual who, as per chart review, meets any of the following criteria prior to the procedure will be excluded from participation in this trial:

- 1. History of HIV
- 2. History of Hepatitis C
- 3. History of diabetes, that in the opinion of the investigator may delay healing
- 4. Current use of systemic corticosteroids

- 5. Active infection of genitals, vagina, cervix, uterus or urinary tract
- 6. Active bacteremia, sepsis or other active systemic infection
- 7. Presence of Sextually Transmitted Infection (STI)
- 8. Evidence of pelvic inflammatory disease (PID)
- 9. Known clotting defects or bleeding disorders
- Hemoglobin < 8 g/dL
- 11. Metastatic disease
- 12. On anticoagulant therapy
- 13. Participation in another interventional trial
- 14. Pregnancy
- 15. Abnormal PAP results that have not been fully evaluated, or in the opinion of the investigator may indicate risk of abnormal vaginal cuff healing
- 16. Co-morbidities that in the opinion of the investigator may indicate risk of abnormal vaginal cuff healing.

Additionally, an individual who meets any of the following intraoperative criteria during hysterectomy will be excluded from participation in this trial:

- 17. Bowel injury during laparoscopic hysterectomy procedure prior to attempted cuff closure
- 18. Bladder injury during laparoscopic hysterectomy procedure prior to attempted cuff closure
- 19. Cases in which, before study randomization, surgeon cannot identify adequate tissue along the cuff to apply suture laparoscopically
- 20. Cases requiring conversion to laparotomy prior to study intervention

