6.3 MEASURES TO MINIMIZE BIAS: RANDOMIZATION AND BLINDING

Variable block size randomization will be employed to assign a vaginal cuff closure method to each subject. At the time of enrollment and after confirmation of intraoperative eligibility, a subject will be randomly assigned treatment (cuff closure) with the test device (Zip-stitch™) or reference device (VICRYL™). This assignment will be provided via sponsor provided randomization envelopes broken down in 2:1 variable block sizes and stratified by site. Treatment allocation blocks will vary from three to six subjects and will be split 2:1 test to reference assignment. This method helps safeguard against a simple randomization generating a smaller than intended test or reference group.

Subjects will be blinded to the cuff closure method they receive during surgery. Because operating surgeons cannot be blinded to the treatment they are providing, this trial cannot be completely double-blinded. Every effort will be made to minimize bias in post-operative data collection. Data collection will be performed by an investigator without access to the blinded to treatment assignment. Treatment assignment will be recorded at the time of procedure in the electronic data capture system. After this point, the investigator collecting follow-up data will be blinded to medical records and treatment group. The operative surgeon cannot be blinded as the performed treatment. They will be available during follow-up as needed but will not participate in data collection for patients that they provided treatment.

Database lock and data un-blinding will take place after completion of the last six-week follow-up visit. Subjects will still participate in the 6 and 12-month visit and extension period call, but data will be unblinded. The data collected at the 12-month telephone visit are limited to pain, dyspareunia, and adverse events. Adverse events are likely to have significant clinical sequelae, and therefore not likely to be forgotten. Pain and dyspareunia are evaluated based on experience in the time frame of the call, and therefore are not affected by recall bias.

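### Section 8.1 allows exclusion just before randomisation because the surgeon decides to suture, a reason missing from 5.2 and the synopsis, and this can shift the non-comparative passing rate by an unknown amount

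*Combined protocol and SAP*

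**What the plan says.** **Exclusions.** Section 8.1 (Intra-Operative Screening) places enrolment or exclusion after uterine excision and just before cuff closure. Its reasons for exclusion at that moment are conversion to laparotomy, the surgeon's "decision to close the cuff using suture with or without" robotic assistance, the subject turning out to meet an exclusion criterion, and other complications. Section 5.2 and the synopsis each give four intra-operative criteria: bowel injury, bladder injury, inadequate tissue, and conversion to laparotomy. The nearest to the 8.1 reason is criterion 19: "Cases in which, before study randomization, surgeon cannot identify adequate tissue along the cuff to apply suture laparoscopically". Section 4.1 ties enrolment to the listed criteria: "Study enrollment will occur during surgery following satisfaction of all intra-operative exclusion criteria".

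**Allocation.** Assignment follows enrolment: "Once a subject has been enrolled, the subject will be assigned to a study group according to study randomization strategy". Section 4.1 adds: "Sealed randomization envelopes stratified by site and in variable block sizes will be provided in a blinded 2:1 ratio". Section 6.3 gives the block sizes: "Treatment allocation blocks will vary from three to six subjects and will be split 2:1 test to reference assignment". It also says: "Because operating surgeons cannot be blinded to the treatment they are providing, this trial cannot be completely double-blinded".

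**Endpoint and population.** The aim stated in 3.1 is to "observe a study population failure rate of less than 5% and is neither statistically-driven nor comparative". Under 9.3 the ITT population holds only enrolled and randomised women.

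**Records.** An Intra-Operative Screening Form is completed during the procedure (8.1), screen-failure details are required (5.4), and women approached but not enrolled go into a screening log (5.5). Section 9 uses none of these in an analysis.

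**The concern.** The 8.1 reason is not shorthand for the 5.2 list, because the same sentence names the meeting of an exclusion criterion as a separate reason. It also differs from criterion 19. That criterion removes women whose cuff tissue is inadequate for laparoscopic suture, while the 8.1 reason removes women whose cuffs the surgeon intends to suture, which is broadly what the reference arm receives.

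In a comparison of arms, exclusion before randomisation acts on both arms alike and mainly limits generalisability. Here the efficacy result is one arm's rate against a fixed figure. If cuffs judged unsuited to clips leave before the envelope is opened, and if those cuffs would have passed clips more often, the observed rate falls and the reference arm offers no correction. A failed closure after randomisation stays in the ITT population (6.5.1, 9.3); an exit before the envelope does not.

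A second, separate matter is that the block sizes are printed in a document intended for the investigators' team. Surgeons who know earlier assignments can sometimes infer the next one, and selection could then differ by arm.

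**Working it through.** **1. The plan's own figure.** Sections 4.1 and 9.2: 35 evaluable test subjects and 10% loss give 35/0.9 = 38.9, rounded up to 39. The 2:1 ratio gives 39/2 = 19.5, rounded up to 20. The total is 59, as stated. Nothing below changes it.

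**2. How many passers the target allows.** The observed rate must be below 5% (3.1).

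- n = 35: 1/35 = 2.9% meets it; 2/35 = 5.7% misses.
- n = 30, 39 and 40: the limit is also one passer (2/30 = 6.7%, 2/39 = 5.1%, and 2/40 = 5.0%, which is not below 5%).
- n = 44 (maximum enrolled): 2/44 = 4.5% meets it; 3/44 = 6.8% misses.

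At the planned size, one woman more or less decides the result.

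**3. Chance of meeting the target at n = 35.** With true rate p, P = (1 − p)^35 + 35p(1 − p)^34. This gives 0.72 at p = 3%, 0.47 at 5%, 0.22 at 8% and 0.12 at 10%. Section 4.2 expects a rate below 10% and gives no point estimate.

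**4. Effect of selection (assumed mix; nothing in the documents fixes it).** Suppose 25% of cuffs are difficult and pass at 20%, and the rest pass at 5%. If a share s of the difficult cuffs is excluded before randomisation, p(s) = [0.25(1 − s)(0.20) + 0.75(0.05)] / (1 − 0.25s).

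| s | p(s) | Chance of meeting the target |
|---|---|---|
| 0 | 0.0875/1 = 8.75% | 0.18 |
| 0.1 | 0.0825/0.975 = 8.5% | 0.19 |
| 0.5 | 0.0625/0.875 = 7.1% | 0.28 |
| 1 | 0.0375/0.75 = 5.0% | 0.47 |

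Four other assumed mixes, each starting at 8% overall (10% of women at 30%, 20% at 25%, 20% at 20%, or 15% at 30%, with the rest set to fit), start at a chance of 0.22. Excluding half of the high-risk women gives 0.30 to 0.36; excluding 80% gives 0.36 to 0.50. If passing is unrelated to the surgeon's choice, the rate does not move. If the excluded women would have passed less often, it rises.

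**5. Predictability of the next arm.** Only sizes 3 (2 + 1) and 6 (4 + 2) in the stated range split exactly 2:1. Assume both sizes are equally likely, 30 subjects per site, block boundaries unknown, and every earlier assignment at the site known. By simulation, about 8% of allocations are certain to be test and 2% certain to be reference, about 10% in all. For about 35% (which includes the certain test ones) the next arm is test with probability above 0.8; the unconditional probability is 2/3.

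**The case against.** The case on the other side has five parts.

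- **Allocation is concealed when the decision is made.** The envelopes are sealed and block size varies. A reader might infer that the surgeon acts knowing the arm; the documents do not support that. Section 6.3 says only that the surgeon cannot be blinded to the treatment being given. At least three surgeons operate, nothing says each sees the others' assignments, and the documents do not say who opens the envelope. This stands, and makes the 10% in step 5 a generous figure.
- **A reader might also infer that the next arm is often predictable.** With one fixed block size and known boundaries, 44% of allocations would be certain in blocks of 3 and 29% in blocks of 6. The plan varies the size, so those shares do not describe it.
- **No passage links cuff difficulty to passing.** Section 4.2 calls passing spontaneous, and a surgeon may choose suture for unrelated reasons. This stands. The rise to 0.47 requires every difficult cuff to be excluded under an assumed mix, and it is the extreme of the range, not an estimate.
- **Safeguards exist.** The form, the screen-failure details and the log would make these exclusions visible. That is right, but they record exclusions without preventing them, and the analysis plan does not bring them to the primary rate. The entry in 8.1 for other complications also has a counterpart in 4.2, which leaves women with unforeseen complications to standard care.
- **Discretion would remain anyway.** Criteria 16 and 19 already rest on the investigator's or surgeon's judgement, so aligning the lists does not end it. That stands too. Section 8.1 also does not say that the suture meant is the reference product.

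The selection argument needs no prediction of the arm. Avoiding cuffs that look unsuited to clips is enough, because the target is not comparative.

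**Conclusion.** The concern holds as an inconsistency with a possible effect on the primary efficacy rate. Section 8.1 admits a reason for exclusion before randomisation that 5.2 and the synopsis do not contain. Women excluded for it never enter ITT, and the 5% target has no comparator to absorb the change in case mix. At n = 35 the result turns on the difference between one and two passers.

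The size and direction of any shift are unknown, because the documents do not show whether surgeons can foresee passing. Under the first assumed mix the gain in the chance of meeting the target runs from 0.01 (0.18 to 0.19, 10% of difficult cuffs excluded) through 0.10 (0.28, half) to 0.29 (0.47, all).

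The printed block sizes are a smaller, independent weakness: about 10% of allocations certain, on the assumptions in step 5.

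A reader might infer that a decision to suture ought not to exclude a woman. The documents contradict each other here and do not settle it. That is a clinical rule for the sponsor.

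**What to change.** 1. Reconcile 8.1, 5.2 and the synopsis so that one list of intra-operative exclusions applies. Which reasons belong on it is for the sponsor to decide.
2. State that the existing Intra-Operative Screening Form, with the reason for any exclusion, is completed before the envelope is opened.
3. Add to 9.4.2 a table of intra-operative exclusions by reason and site, reported beside the primary passing rate.
4. Move the block sizes from 6.3 to a restricted randomisation document; the protocol need only say that block sizes vary within site.

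The cost is minor wording and one extra table. The sample size stays at 59. Blocks of 6 and 9 are optional: on the assumptions in step 5 they lower the certain share from about 10% to between 5% and 6%, at the price of reprinted envelopes and a larger possible imbalance with only 20 reference subjects planned.
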